## 8. STUDY POPULATION PARAMETERS

Listings of all study population parameters will be done for the primary and exploratory ITT populations and summaries will be done for the primary mITT population. Some summaries may also be done for other analysis populations defined in [Section 6](#). Study population parameters to be listed and summarized are described below.

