## 6. ANALYSIS POPULATIONS

The following analysis populations are defined for the trial:

**Primary Safety Population:** All subjects in the Primary Randomization Cohort who received the IP. Subjects will be summarized and analyzed per treatment actually received, regardless of their randomization assignment.

**Primary Intent-to-Treat (ITT) Population:** All subjects in the Primary Randomization Cohort who were randomized. Subjects will be summarized and analyzed per their randomization assignment, regardless of the treatment actually received.

**Primary Modified Intent-to-Treat (mITT) Population:** For a given efficacy parameter, all subjects in the Primary Randomization Cohort who received the IP, had a baseline observation and at

least one post-baseline observation. Subjects will be summarized and analyzed per their randomization assignment, regardless of the treatment actually received.

Per Protocol Population: Subjects in the Primary Randomization Cohort with no major protocol violations at end of study (EOS). The list of subjects with major protocol violations will be compiled in a blinded fashion prior to database lock at EOS. For the analysis of the primary efficacy endpoint based on the per protocol population, a sensitivity analysis will be done to evaluate the effect of excluding subjects randomized in the wrong cohort or the wrong stratum from the per protocol population; i.e., subjects incorrectly randomized in the Exploratory Randomization Cohort would be excluded from the per-protocol sensitivity analysis, as would subjects randomized in the wrong stratum based on time since index MI (recent vs. chronic).

Exploratory Safety Population: All subjects in the Exploratory Randomization Cohort who received the IP. Subjects will be summarized and analyzed per treatment actually received, regardless of their randomization assignment.

Exploratory ITT Population: All subjects in the Exploratory Randomization Cohort who were randomized. Subjects will be summarized and analyzed per their randomization assignment, regardless of the treatment actually received.

Exploratory mITT Population: For a given parameter, all subjects in the Exploratory Randomization Cohort who received the IP, had a baseline observation and at least one post-baseline observation. Subjects will be summarized and analyzed per their randomization assignment, regardless of the treatment actually received.

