### **8.7 IP Administration**

Details of IP administration will be listed. Parameters to be summarized will include successful completion of IP administration, reason for non-completion, total volume infused, whether or not the full dose was administered, final TIMI flow score per artery infused, and indicators for a series of events occurring during IP administration and a series of events within 24 hours of IP administration. Such events will also be recorded as AEs and will also appear in AE listings and summaries.

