## 8.9 Subject Disposition

A listing of subject disposition will include dates of randomization and IP administration (or attempt), whether or not the subject completed the Month 12 visit, subject-level EOS date, reason for study discontinuation (if applicable), and whether or not the subject consented to annual LTFUP. Frequencies and percentages of subjects who discontinued and reasons for discontinuation as well as duration of follow-up will be summarized. Duration of follow-up will be calculated as:

$$\text{duration} = \text{date of last known status} - \text{date of infusion} + 1$$

where date of last known status is the maximum date among AE start and end dates, concomitant medication start and stop dates, visit dates (including unscheduled visits), and EOS date.

The summary table will include a p-value for treatment group comparison of discontinuation for any reason and, if appropriate, for duration of follow-up based on a log rank test.

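### The SAP's default population for the disposition table and its discontinuation test (mITT) leaves out randomised subjects never infused and those who leave before a qualifying post-baseline observation

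*SAP*

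**What the plan says.** SAP Section 8 sets one rule for all study-population parameters. Listings use the ITT populations, but "summaries will be done for the primary mITT population". The next sentence, which points to Section 6, adds an option ("Some summaries may also be done for other analysis populations defined in") without naming a table or a population.

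Section 8.9 (Subject Disposition) summarises discontinuations, reasons and duration of follow-up. "The summary table will include a p-value for treatment group comparison of discontinuation for any reason", and a log-rank test of follow-up duration is added if appropriate. Duration is counted from the infusion date. Neither Section 8.9 nor the entry for Table 14.1.2 in Appendix C names another population.

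Section 8.7 (IP Administration) falls under the same default: "Parameters to be summarized will include successful completion of IP administration, reason for non-completion", among other items. It states no p-value.

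Section 6 opens its mITT definition with "For a given efficacy parameter, all subjects in the Primary Randomization Cohort who received the IP, had a baseline observation". It then requires one or more values after baseline as well, and analyses subjects by randomised arm. Section 6 also defines a Primary ITT population: "All subjects in the Primary Randomization Cohort who were randomized". Section 7.3 already gives the randomisation date as the ITT reference date.

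**The concern.** A disposition table shows who entered, who left, when and why, by arm. If membership of the table requires having been infused and having stayed long enough to provide a post-baseline value, the comparison of discontinuation is conditioned on not having discontinued early.

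The documents expect such subjects. Protocol Section 7.1 has sites randomise at least three working days before the scheduled infusion and requires eligibility to hold afterwards. Protocol Section 7.2.1 provides that a subject with a clinically significant coronary occlusion on the day of infusion is not infused, is withdrawn and is not followed. SAP Section 7.7 has a study-day rule for untreated subjects, and SAP Section 9 says some ITT subjects may lack both the Month 6 and the Month 12 change.

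The primary efficacy analysis is a likelihood analysis in mITT under missing at random, and SAP Section 9 concedes that this assumption cannot be tested and that subjects with poorer outcomes may be more likely to miss assessments. Discontinuation by arm among all randomised subjects is one of the few descriptive checks a reader has on it.

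**Working it through.** **1. Who is outside the default table.** The mITT definition imposes three conditions.

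- *Received the IP.* This removes every randomised subject who was not infused, including those withdrawn on Day 0.
- *Baseline observation.* This should remove few, since baseline is measured at screening.
- *At least one post-baseline observation.* This removes infused subjects who leave before providing one.

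**2. The denominator is not fixed.** The definition is specific to each efficacy parameter, and Section 8 does not say which one applies to disposition.

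- Infarct size: protocol Section 9.2 schedules follow-up MRI at 6 and 12 months only, and the SAP's Month 6 analysis window opens on Day 136. An earlier leaver qualifies only with an early-termination MRI.
- NT-proBNP: scheduled at the Week 2 visit (protocol Section 7.3.1), so nearly all infused subjects would qualify.

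The same trial could thus report different discontinuation rates from the same SAP text.

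**3. The plan's own figure.** The protocol randomises 103 to obtain 93 with complete 12-month data at 10% non-completion: 103 × (1 − 0.10) = 92.7, about 93. This reproduces and is not in dispute. It gives about 103 − 93 = 10 non-completers. The arms are 69 CAP-1002 and 34 placebo (protocol synopsis, Study Population).

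**4. Illustration.** For each arm, the ITT rate is (early + late exits) / randomised. The mITT rate is late exits / (randomised − early exits), where early means before a qualifying observation. Tests are two-sided Fisher exact. The arm splits and timings are assumptions; the documents give neither.

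| Assumed exits (CAP-1002 : placebo) | ITT | mITT |
|---|---|---|
| 10 early, 2:8 | 2/69 (2.9%) vs 8/34 (23.5%), p = 0.002 | 0/67 vs 0/26, p = 1 |
| 10 early, 10:0 | 10/69 (14.5%) vs 0/34, p = 0.028 | 0/59 vs 0/34, p = 1 |
| 5 early, 0:5; 5 late, 3:2 | 3/69 (4.3%) vs 7/34 (20.6%), p = 0.014 | 3/69 (4.3%) vs 2/29 (6.9%), p = 0.63 |
| 10 early, 9:1 | 9/69 (13.0%) vs 1/34 (2.9%), p = 0.16 | 0/60 vs 0/33, p = 1 |
| 10 early, 7:3 | 7/69 (10.1%) vs 3/34 (8.8%), p = 1 | 0/62 vs 0/31, p = 1 |
| 10 late, 2:8 | 2/69 (2.9%) vs 8/34 (23.5%), p = 0.002 | identical |

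The first three rows lose a significant imbalance. In the fourth and fifth there was none to lose, although the rates still fall to zero. In the last row nothing changes.

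**5. Follow-up duration.** Section 8.9 computes date of last known status − date of infusion + 1. For a subject never infused this has no value, so changing the population alone would not suffice; the start date must change as well.

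**The case against.** The case against has real force on several points.

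- *Early exits are not always lost.* Protocol Section 7.9 asks sites to attempt the Month 12 testing at early withdrawal, and the Schedule of Events puts cardiac MRI in the combined Month 12/early-termination column. The mITT definition has no visit window, so such an MRI keeps the subject in. A reader might infer that the table cannot show any attrition before Month 6; the documents do not support that, both for this reason and because no parameter is named.
- *The count can be recovered.* Section 8.1 reports the size of each analysis population, tables are shown by arm and stratum, and the disposition listing, with reasons, is on ITT. This stands for the number excluded. It supplies neither a summary of their reasons nor a test.
- *Safety events are covered elsewhere.* Section 8.7 sends infusion events to the adverse-event summaries as well, and Sections 10 and 10.3 use the safety population for events within 24 hours, deaths, and adverse events leading to discontinuation. It would therefore be wrong to infer that the trial's reporting as a whole understates procedural complications. These tables do not cover withdrawals for other reasons or subjects never infused.
- *Infusion completion.* A reader might infer that it is formally tested in mITT. Section 8.7 states no test; one could arise only through the general rule in Section 7.3. Subjects with an incomplete infusion and a later observation stay in the table.
- *Missing data.* SAP Section 9 commits to a missing-not-at-random sensitivity analysis of the primary endpoint, so the disposition p-value is not the plan's only safeguard.
- *The ten are not ten discontinuations.* The 10% refers to incomplete 12-month data. Subjects with an MRI contraindication remain in the study under protocol Sections 7.3.5 and 7.3.6.

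The option to use other populations does not answer the point, because it commits to nothing.

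**Conclusion.** The point holds as a defect in a stated rule. Followed as written, the SAP computes the discontinuation rate, its p-value and any log-rank test of follow-up in a population that excludes randomised subjects never infused and infused subjects without a qualifying observation, with a denominator that depends on an unnamed parameter.

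The size runs from no effect, if every exit follows a qualifying observation, to the loss of all early exits; on the planning figure the upper end is about 10 of 103. Where in that range the trial would fall depends on timing, arm split, early-termination MRIs and the parameter chosen, none of which the documents fix.

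The stronger reading, that differential dropout disappears from the report, is not supported: later dropout is shown and tested, and early loss can be counted from the population sizes and the ITT listing. The defect does not alter the primary efficacy or primary safety test. It weakens the table by which a reader would judge attrition, and it should be corrected because the remedy is simple and the needed population is already defined.

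**What to change.** In SAP Section 8, replace the single mITT default as follows.

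1. Summarise 8.8 Subject Study Progress (Table 14.1.1) and summarise and test 8.9 Subject Disposition (Table 14.1.2) in the Primary ITT population by randomised arm.
2. In Table 14.1.2, add a row for subjects randomised but not infused, with reasons, and report there those catheterised but not infused. They cannot be placed in the Primary Safety population, which requires receipt of the IP.
3. For that table, count follow-up duration from randomisation, consistent with the ITT reference date in Section 7.3.
4. Summarise 8.7 IP Administration (Tables 14.1.8.1 to 14.1.8.3) in the Primary Safety population.

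The cost is SAP wording, population flags in the affected table programs and one changed start date. No new data are needed, since the ITT listings already carry these subjects.

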### 8.1 Analysis Populations

The analysis populations defined in [Section 6](#) will be described in terms of the identification of subjects in each population and the frequency distribution of each population.

### 8.2 Eligibility and Informed Consent

Eligibility and informed consent parameters will be listed and will include protocol version and dates of informed consents (general, biomarkers). Inclusion and/or exclusion criteria that were not met will be listed, as will details on any waivers granted. Satisfaction of inclusion/exclusion criteria will be summarized.

### **8.3 Demographics**

Subject demographic parameters will be study site, age, sex, race, and ethnicity and will be listed and summarized. Summary tables will include p-values for treatment group differences. Age will be computed in SAS as follows:

$$\text{AGE} = \text{floor}((\text{intck}(\text{'MONTH'}, \text{bdt}, \text{rdt}) - (\text{day}(\text{rdt}) < \text{day}(\text{bdt}))) / 12)$$

where bdt = birth date in SAS date format and rdt = reference date in SAS date format.

### **8.4 Medical History**

General medical history and cardiac history will be listed and summarized separately. Summaries will include frequencies and percentages of subjects with each condition. Differences in medical and cardiac history by treatment group will be analyzed and p-values (for frequencies only) will be included in the summary table.

### **8.5 Computerized Tomography of the Chest, Abdomen and Pelvis**

A computerized tomography (CT) of the chest, abdomen and pelvis is performed at the screening visit to ensure that there are no clinically significant pre-existing abnormalities to internal organs or presence of tumors or cancer. Parameters will be listed and will include whether or not the CT was done, date of the CT, and the result (normal, abnormal not clinically significant, abnormal clinically significant).

### **8.6 Laboratory Screens and Immunogenicity Testing (HLA)**

Laboratory screens will include human immunodeficiency virus (HIV), hepatitis B surface antigen (HBsAg), hepatitis C virus (HCV), glycosylated hemoglobin (HbA1c), and serum pregnancy. Laboratory screens and HLA will be listed and summarized.

### **8.7 IP Administration**

Details of IP administration will be listed. Parameters to be summarized will include successful completion of IP administration, reason for non-completion, total volume infused, whether or not the full dose was administered, final TIMI flow score per artery infused, and indicators for a series of events occurring during IP administration and a series of events within 24 hours of IP administration. Such events will also be recorded as AEs and will also appear in AE listings and summaries.

### **8.8 Subject Study Progress**

A listing of subject study progress will show dates of screening, informed consent, randomization, IP administration, study visits, and EOS. Number of subjects who completed each visit will be summarized.

## 8.9 Subject Disposition

A listing of subject disposition will include dates of randomization and IP administration (or attempt), whether or not the subject completed the Month 12 visit, subject-level EOS date, reason for study discontinuation (if applicable), and whether or not the subject consented to annual LTFUP. Frequencies and percentages of subjects who discontinued and reasons for discontinuation as well as duration of follow-up will be summarized. Duration of follow-up will be calculated as:

$$\text{duration} = \text{date of last known status} - \text{date of infusion} + 1$$

where date of last known status is the maximum date among AE start and end dates, concomitant medication start and stop dates, visit dates (including unscheduled visits), and EOS date.

The summary table will include a p-value for treatment group comparison of discontinuation for any reason and, if appropriate, for duration of follow-up based on a log rank test.

## 9. EFFICACY ANALYSIS

All efficacy parameters will be listed for the primary ITT population and summarized for the mITT population. The primary analysis of primary and secondary efficacy endpoints will be done using the primary mITT population. Secondary analyses may be done using the other analysis populations defined in [Section 6](#) or in subgroups defined in [Section 7.4](#). In addition, “last observation” analyses will be done for certain parameters for which some subjects’ final assessments were done too late to be included in the Month 12 analysis window.

Analyses of changes from baseline will be done using general linear models with baseline values as covariates. Analyses of the effect of treatment group, analysis window (e.g., baseline, Month 6, Month 12), and their interaction will be done using mixed effects linear regression, with subject as a random effect, analysis window, and treatment group as fixed effects, and baseline as a fixed-effect covariate. For “last observation” analyses, “time” as a continuous covariate will be substituted for analysis window. Study site may also be included as a random effect if there is evidence of correlation within study sites (per the interclass correlation coefficient from the unconditional model) and/or if doing so appreciably improves the model fit (e.g., per Akaike’s Information Criterion). Other covariates that may be considered include age (< 65 vs.  $\geq$  65 years), sex, race (African-American vs. other), baseline 6MWT, baseline LVESV, baseline NT-proBNP, and DSA (as an indicator variable). Residuals will be evaluated for substantial departure from normality and independent and constant variance and appropriate remedies (e.g., data transformations, detecting and assessing the influence of outliers, alternative analytical approaches) will be attempted when necessary. An unstructured covariance will be the default covariance structure but other structures (e.g., compound symmetry) may be used to evaluate sensitivity to the choice of structure or, if study site is included as a random effect, to achieve convergence.

Assuming missing observations are “missing at random” (MAR), i.e., the fact that they are missing is unrelated to the missing variable but can be related to another variable on which data have been collected, the maximum likelihood (ML) approach is able to handle subjects with

either Month 6 or Month 12 changes from baseline missing, but not both. Therefore, for analyses based on the mITT population, missing data will be addressed using ML. For analyses based on the ITT population, in which some subjects may have both Month 6 and Month 12 changes from baseline missing, multiple imputation will be used based on all observations and will use a fully conditional specification method with 20 burn-in iterations and the regression method of imputation. Variables in the imputer's model will be baseline observation (because baseline is used as a covariate in analyses), Month 6 change from baseline, Month 12 change from baseline, and treatment group. Because the MAR assumption is not testable, and because it seems possible that subjects with poorer outcome may be more likely to miss trial assessments, a sensitivity analysis under a "missing not at random" (MNAR) assumption will be done (for the final analysis only) of the primary efficacy endpoint in which multiple imputation will use the pattern-mixture model approach to address missing values; i.e., the imputation will be based on a pre-specified subset of subjects. For this MNAR analysis, only those subjects who had implantable cardioverter defibrillators (ICDs) inserted during the trial. Because very few missing observations are expected in this trial, 5 imputed data sets will be used for all analyses using multiple imputation.

A closed testing procedure will be used for the primary efficacy analysis only (see [Section 2.3.5](#)) and will be done as follows:

1. Let  $p_f$  and  $p_s$  be the p-values from the tests of the individual null hypotheses involving the full group and the subgroup, respectively; tests will be based on least squares (LS) means comparisons.
2. Let  $t_{max} = \max(t_f, t_s)$ , where  $t_f$  and  $t_s$  are the t-statistics from the full group and subgroup analyses in (1) above.
3. Let  $r$  = the correlation between  $t_f$  and  $t_s$ , estimated by the ratio of SDs of the treatment effect estimates in the full group and subgroup.
4. Let  $p_{inter}$  be the p-value from the test of the intersection hypothesis using Dunnett's test; specifically,  $p_{inter} = 1 - \text{probnorm}(t_{max}, t_{max}, r)$ .

Then, if  $p_{inter} < 0.025$  and either  $p_f < 0.025$  or  $p_s < 0.025$  (with treatment effect favoring CAP-1002), the test of treatment effect for the primary efficacy endpoint will be considered statistically significant.

For all non-primary efficacy analyses, tests of treatment effect will be based on comparisons of LS means with no adjustment for multiple comparisons.

A descriptive correlation analysis will be done for all pairs of tissue-based and functional efficacy endpoints (i.e., MRI outcomes) using Pearson's or Spearman's correlation coefficient.

Efficacy parameters are described below.

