The secondary efficacy objective is to evaluate whether administration of CAP-1002 by intracoronary infusion may result in other left ventricular structural or functional cardiac benefits for subjects with ischemic left ventricular dysfunction and a previous MI. Also evaluations will investigate whether administration of CAP-1002 may result in clinical or biomarker benefits for subjects with ischemic left ventricular dysfunction and a previous MI.

Study Design:

In Phase 2, the Primary Randomized Cohort will enroll up to approximately 103 subjects with a previous myocardial infarction (MI) and resultant ischemic left ventricular dysfunction meeting all inclusion and no exclusion criteria. The Primary Randomized Cohort will include the Recent and Chronic MI strata (n= approximately 51-52 per stratum). These 103 subjects will be randomized in a double-blind fashion to receive either CAP-1002 or placebo (collectively referred to as Investigational Product [IP]) in a 2:1 ratio favoring CAP-1002 to achieve up to 93 subjects with complete 12 month data (assumes 10% non-completion rate and 103 subjects randomized). After completion of the screening procedures and meeting all inclusion and exclusion criteria, study subjects will be randomized to receive CAP-1002 or placebo administered via intracoronary infusion. All subjects in the Primary Randomized Cohort will be followed at week 2 and at months 1, 3, 6 and 12 after planned CAP-1002 or placebo infusion. Efficacy will be assessed at all specified post-infusion visits, with the 12 month visit being the primary efficacy endpoint. An administrative interim analysis of the final 6 month data will be performed when all subjects in the Primary Randomized Cohort have completed the 6 month visit to assist in planning Phase III studies.

The double-blind, placebo-controlled design of the Primary Randomized Cohort will maximize

the study's ability to assess both safety and efficacy, as both may be subject to bias from the perspective of Investigators and subjects.

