3 INVESTIGATIONAL PLAN

3.1 Overall Study Design and Plan

In Phase 2, the Primary Randomized Cohort will enroll up to approximately one hundred three (103) subjects with a previous myocardial infarction (MI) and resultant ischemic left ventricular dysfunction meeting all inclusion and no exclusion criteria. The Primary Randomized Cohort will include the Recent and Chronic MI strata. These approximately 103 subjects will be randomized in a double-blind fashion to receive either CAP-1002 or placebo (collectively referred to as Investigational Product [IP]) in a 2:1 ratio favoring CAP-1002 to achieve 93 subjects with complete 12 month data (assumes 10% non-completion rate). Subjects may sign consent and start the screening process immediately post-MI (e.g., acute admission at hospital). The following assessments will be permitted within 28 days immediately following the subject's MI: signing ICF, review of medical history, review of concomitant medications, and collection of laboratory samples required for assessment of study eligibility criteria (e.g., eGFR, HbA1c, hepatitis serology, HIV serology, LFTs, hematocrit, WBC, and platelet count). All other screening tests, including the subject's cardiac MRI and CT (chest, abdomen, pelvis), must be conducted greater than 28 days post-MI. Infusion must occur within 28 days of the first screening procedure that is performed greater than 28 days post-MI. Relevant safety laboratory sample collections (e.g., chemistry, hematology, urinalysis) may need to be repeated as they must be obtained within 28 days of the subject's infusion. A subject that rescreens for any reason may be required to repeat all protocol safety procedures (excluding CT of the chest, abdomen and pelvis if previously conducted) if the safety procedures were originally conducted greater than 28 days prior to the subject's infusion. A subject that rescreens for any reason may be required to repeat all protocol efficacy procedures including the cardiac MRI unless: a) the subject's efficacy procedures including baseline cardiac MRI were conducted within 28 days of infusion; or, b) the subject's efficacy procedures including baseline cardiac MRI were conducted \geq 60 days post-MI **and** within 60 days of infusion. Additional instructions are included in protocol Section 7 and Appendix I (Schedule of Events). After completion of the screening procedures and meeting all inclusion and exclusion criteria, study subjects will be randomized to receive CAP-1002 or placebo administered via intracoronary infusion. All subjects in the Primary Randomized Cohort will be followed at week 2 and at months 1, 3, 6 and 12 after planned CAP-1002 or placebo infusion. Efficacy will be assessed at all specified post-infusion visits, with the 12 month visit being the primary efficacy endpoint. An administrative interim analysis of the final 6 month data will be performed when all subjects in the Primary Randomized Cohort have completed the 6 month visit to assist in planning Phase III studies.

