9.2 Determination of Sample Size

In total, a maximum of approximately one hundred thirty-four (134) subjects with a MI and resulting ischemic left ventricular dysfunction meeting all inclusion and no exclusion criteria will be enrolled. The first fourteen (14) subjects (7 Recent MI and 7 Chronic MI) will receive CAP-1002 open-label and will be designated as the Safety Cohort. The approximate maximums of one hundred three (103) subjects in the Primary Randomized Cohort (51-52 Recent MI and 51-52 Chronic MI) and the up to 17 subjects in the Exploratory Randomized Cohort will begin to enroll only after DSMB review of the Safety Cohort data and recommendation to proceed. These approximately 120 subjects in the Primary Randomized Cohort and Exploratory Randomized Cohort will be independently randomized in a double-blind fashion to receive either CAP-1002 or placebo in a 2:1 ratio, favoring CAP-1002 to achieve approximately up to 93 subjects with complete 12 month data in the Randomized Cohort. A balancing algorithm will be used to ensure site-specific balancing to the 2:1 allocation after stratifying for prior MI.

The Safety Cohort was evaluated once all subjects reached the primary safety endpoint assessed at the 1 month visit. With n=14, if no significant safety events are observed, the one-sided 95% upper bound for the true rate of significant events would be < 20%. The DSMB conducted a review of the Safety Cohort data and made a recommendation to proceed with randomization of the next 120 subjects. Efficacy and safety will be assessed at all post-screening visits, although

MRI testing will only be completed at 6 and 12 months; the 12 month visit is the primary efficacy endpoint.

Historical Data

The CADUCEUS and ALLSTAR Safety Cohort data provide some background for planning sample size to test for efficacy. The efficacy endpoints in the CADUCEUS study and in the ALLSTAR Safety Cohort included the relative change in the Month 6 and 12 outcomes relative to baseline as judged by MRI assessment of infarct size (measured in %). Assumptions used for power calculations are summarized below in [Table 4](#) with the relative change displayed as a percent improvement from baseline. The ALLSTAR Safety Cohort was used for the assumed means and SDs and CADUCEUS was used for the treatment effect in Chronic MI patients relative to Recent MI.

Table 4. Sample Size Assumptions

| | Month 6 | | Month 12 | |
|------------------|---------|-------|----------|-------|

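### The SAP's imputation model omits the Recent/Chronic stratum, which biases the optional ITT analysis slightly, and its five imputations rest on a missing-data premise that the protocol contradicts

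*SAP*

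**What the plan says.** SAP section 9 (Efficacy Analysis) handles missing data in three ways.

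- **mITT, the primary analysis:** maximum likelihood, with no imputation.
- **ITT:** "multiple imputation will be used based on all observations". The listed predictors start with "Variables in the imputer's model will be baseline observation" and end with "Month 6 change from baseline, Month 12 change from baseline, and treatment group". Stratum is not listed, and nothing says that imputation is run separately by stratum. Analyses in populations other than mITT are optional.
- **Missing-not-at-random (MNAR) sensitivity analysis of the primary endpoint:** multiple imputation based only on subjects who received an ICD during the trial. The SAP commits to this one for the final analysis.

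One rule sets the number of imputations for the last two: "Because very few missing observations are expected in this trial, 5 imputed data sets will be used for all analyses using multiple imputation". No random seed is named.

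The protocol expects more loss than that. Section 3.1 randomizes about 103 subjects "to achieve 93 subjects with complete 12 month data (assumes 10% non-completion rate"), and the synopsis repeats the assumption: "assumes 10% non-completion rate and 103 subjects randomized".

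Stratum is central elsewhere. Randomization is within stratum (SAP section 5), the Recent subgroup is one of the two primary hypotheses (SAP 2.3.5), every table and figure is shown by stratum (SAP 7.4), and Table 1 of the SAP (Table 4 of the protocol) assumes Month 12 reductions of 14.70 in Recent and 7.35 in Chronic.

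**The concern.** An imputation model should contain the structure that the analysis will examine. The SAP accepts this for baseline, which it includes because baseline is an analysis covariate. Stratum and its interaction with treatment qualify on the same ground. Without them, a missing Recent subject on CAP-1002 is imputed from the average effect over both strata, and each stratum's estimate drifts toward the other's.

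Few imputations are tolerable when little is missing. At the loss the protocol plans for, the pooled estimate and p-value from five data sets depend noticeably on the random draw. What is at stake is how far a reader can rely on the supporting ITT result by stratum, and on the MNAR sensitivity result, if either falls near a conventional significance limit.

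**Working it through.** **Inputs.** 103 subjects in two strata ("51-52 Recent MI and 51-52 Chronic MI"), randomized 2:1, so 34/17 Recent and 35/17 Chronic; Month 12 means 14.70, 7.35 and 0 with SD 10 (SAP Table 1); 10% non-completion (protocol 3.1). Assumed, because the documents do not give them: data missing completely at random at 3%, 10% or 20%; baseline 22 (SD 5), unrelated to outcome; Month 6 to Month 12 correlation 0.5. The correlation matters only where Month 6 is observed and used.

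**1. The plan's own figure.** 103 × 0.90 = 92.7, so 93 completers. The protocol is consistent, and it implies about 10 subjects without Month 12 data.

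**2. Size of the pull, by hand.** With equal strata the pooled effect is (14.70 + 7.35)/2 = 11.03, which is 3.68 below the Recent effect. The expected bias is the fraction missing times this gap: 0.10 × 3.68 = 0.37 points, or 0.20 × 3.68 = 0.74. Chronic moves up by the same amount. The standard error of the Recent effect is 10 × √(1/34 + 1/17) = 2.97, so 0.37 is 0.12 standard errors, or 2.5% of 14.7.

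**3. The same by simulation.** 1,500 trials per row, five imputations, Bayesian regression imputation, ANCOVA, Rubin's rules. Cells show the estimate without / with stratum and stratum-by-treatment in the imputer.

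| Missing | Month 6 | Recent (true 14.70) | Chronic (true 7.35) | Full group | Power, Recent |
|---|---|---|---|---|---|
| 3% | also missing | 14.52 / 14.63 | 7.42 / 7.32 | 10.92 / 10.92 | 0.996 / 0.996 |
| 10% | also missing | 14.34 / 14.76 | 7.68 / 7.31 | 10.96 / 10.98 | 0.996 / 0.995 |
| 10% | observed | 14.47 / 14.73 | 7.76 / 7.50 | 11.07 / 11.06 | 0.997 / 0.997 |
| 20% | also missing | 13.86 / 14.64 | 8.15 / 7.37 | 10.97 / 10.96 | 0.975 / 0.979 |
| 20% | observed | 14.12 / 14.75 | 8.02 / 7.43 | 11.02 / 11.03 | 0.989 / 0.989 |

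The mean within-trial difference for Recent is 0.42 (Month 6 also missing) or 0.26 (observed) at 10%, and 0.78 or 0.63 at 20%.

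**4. Monte Carlo error, by hand.** At 10% missing, about 10% of the total variance comes from the imputation. The pooled estimate then has a Monte Carlo SD of about √(0.10/m) standard errors: 0.14 for m = 5 and 0.045 for m = 50. Around z = 1.96, a band of ±1.645 of these SDs runs from z = 1.73 to 2.19 (one-sided p 0.042 to 0.014) for m = 5, and from 1.89 to 2.03 (p 0.030 to 0.021) for m = 50.

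**5. The same by simulation.** Effects were scaled to 45% of plan so that borderline results were common. Sixty data sets with a converged one-sided p of 0.02 to 0.03 were kept per scenario and imputed repeatedly with the SAP's predictors. At 10% missing, with both visits missing:

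| m | Recent p, central 95% of seeds | Full-group p, central 95% | Seeds on the minority side of 0.025 (Recent / full) |
|---|---|---|---|
| 5 | 0.013–0.055 | 0.012–0.053 | 37% / 40% |
| 20 | 0.018–0.037 | 0.017–0.035 | 27% / 30% |
| 50 | 0.021–0.032 | 0.020–0.030 | 19% / 22% |
| 100 | 0.022–0.030 | 0.021–0.028 | 13% / 16% |

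A separate simulation, summarized by 5th and 95th percentiles, gave roughly 0.013–0.047 for m = 5 and 0.019–0.029 for m = 50. At only 3% missing, m = 5 still gives 0.019–0.037 for Recent, with about 25% of seeds on the minority side.

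**The case against.** The case for leaving the text alone is that no decision rests on it. The primary test is mITT with maximum likelihood; ITT analyses are optional; the closed test at one-sided 0.025 belongs to the primary efficacy analysis only. The stratum bias is about a tenth of a standard error, costs no power, is conservative for Recent under Table 1, and disappears if the strata share one effect. Under the planned Recent effect the expected z is 14.7/2.97 = 4.9, so a p near 0.02 (z about 2.05) would be almost 3 standard errors low, and so rare.

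Most of this stands, and it rules out three stronger readings that a reader might infer.

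- **That the primary test of the Recent hypothesis is biased.** That test does not use imputation.
- **That the trial's success could turn on a seed.** The SAP attaches no success criterion to the ITT or MNAR results. The 0.025 line above is a reference point: in the favorable direction it is the same boundary as the SAP's default two-sided 0.05.
- **That the analysis cannot be reproduced.** A recorded seed reproduces it exactly. The problem is Monte Carlo error, together with the absence of a named seed.

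Two parts of the objection do not carry. The pull is conservative for Recent only if Recent is the larger effect; with the order reversed it would inflate Recent. And the number of imputations is not confined to an optional analysis, since it also governs the MNAR analysis that the SAP commits to.

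**Conclusion.** The point holds as a minor one with two parts of unequal weight. Omitting stratum is inconsistent with the rest of the plan, but the pull is small, and it rests on Table 1's unequal effects and on data missing completely at random. The choice of five imputations matters more: its stated reason conflicts with the protocol's 10% non-completion, and near a threshold the p-value moves materially with the seed. It matters only for borderline results. The seed ranges were computed for the ITT-type imputation. The MNAR analysis falls under the same rule, but its Monte Carlo error was not computed, because the number of subjects with a new ICD is not in the documents.

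**What to change.** - **ITT imputation model:** add stratum and stratum-by-treatment. This is preferable to imputing separately by arm within stratum, because the Recent placebo cell would have only about 17 × 0.90 = 15 observed subjects. SAP 7.4 derives the analysis stratum from the infusion date, so say which stratum applies to randomized subjects who were never infused.
- **Number of imputations:** at least 50 for every multiple-imputation analysis, including the MNAR one, and 100 or more if a result is borderline, since the range at 50 still straddles 0.025. Pre-specify the seed.
- **Rationale:** replace the expectation of hardly any missing data with one consistent with 10% non-completion.

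The cost is a short SAP edit before database lock and a little computing time. Stratum is already recorded at randomization, so no new data, visits or subjects are needed.
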